**Figure 2: Trial flow chart**

Abbreviations: N: number of participants in corresponding treatment arm; PQP: Piperaquine; PYR: Pyronaridine.

As long as the data from the sentinel group demonstrate acceptable safety and tolerability, the participants in the non-sentinel group will be discharged on Day 5, but this decision will be made by the Safety Review Committee (SRC) (See Table 7). The Day 6 OP visit will apply to the non-sentinel group only.

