**Table 7: Adaptive protocol features**

Adaptive Study Design Areas	Features	Limits
Sentinel/ subgroup dosing	1. Cohorts may be split into sub-groups.	
I. A mandatory sentinel dosing strategy of dosing four participants from treatment arm 1, and two participants from each of treatment arms 2, 3 and 4, will be used. There will be a total of ten participants in the sentinel dosing. The remaining participants can be dosed if safety and tolerability data up to 15 days post first dose is acceptable.
 
II. The participants in the sentinel group will all be dosed in parallel. If they are successfully dosed (i.e. it is deemed safe to dose the other participants), the remaining 30 participants may all be dosed at the same time, in parallel, or they may be divided into two or more dosing groups, with the groups being dosed on different days. Each dosing group would contain a minimum of two participants from each of the four treatment arms, to maintain blinding and avoid bias (See Table 12).

Flexible Cohort Sizes	2. Withdrawn participants can be replaced at the discretion of the sponsor and PI. 3. Replacement participants may be enrolled in an ongoing treatment group or dosed together as a group or dosed separately, except for	
I. The maximum extension is 100 % of the original treatment group.
 
II. Trial specific AR rules (Section 4.4) apply.

Adaptive Study Design Areas	Features	Limits
	
those participants in the sentinel group.
 
4. The number of participants in a treatment group can be extended to gather further information.
	

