#### **3.4.4 Precautions to be applied for dosing between participants in sentinel group and participants in the main group**

A mandatory sentinel dosing strategy of dosing ten participants will be used to provide safety assessment. The sentinel group will consist of four participants from treatment arm 1 and two participants from each of treatment arms 2, 3 and 4. Blinded safety data up to Day 15 in the sentinel group will be reviewed by a Safety Review Committee (SRC) prior to dosing the 30 remaining participants. If safety and tolerability is acceptable from participants within the sentinel group, the remaining participants of each treatment arm may be dosed.

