## 3.3 Randomisation and Blinding

### Subject Randomisation

All subjects in this trial will be assigned to a treatment regimen according to a randomisation schedule generated by a statistician using PROC Plan. Details regarding the unique screening and subject number will be included in the SOM.

Eligible subjects will be randomly assigned in a 2:1:1:1 ratio to one of four treatment arms on Day 1, at the point of dosing. Treatment arms are outlined below:

- Treatment 1 (N=16): PYR + PQP
- Treatment 2 (N=8): PYR + placebo for PQP
- Treatment 3 (N=8): placebo for PYR + PQP
- Treatment 4 (N=8): placebo for PYR + placebo for PQP.

Sentinel dosing (N=10) will occur: four subjects for treatment arm 1, and two subjects from each of treatment arms 2, 3 and 4, will be dosed before the remaining subjects of each treatment arm are dosed together (see protocol Section **Error! Reference source not found.**).

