### Per timepoint analysis

For all quantitative ECG parameters, descriptive statistics will be given for the change from baseline. In addition, for QTc, a linear model with the two treatments (PYR and PQP) and their interaction as factors and baseline as covariate will be fitted for each timepoint; the difference between each of the active treatments and placebo will be estimated based on this model; and two-sided 90% confidence intervals (CI) will be given.

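### The per-timepoint QTc model leaves out dosing cohort, although treatment numbers are fixed within the sentinel and main cohorts, so any cohort difference in QTc change widens the 90% confidence intervals

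*SAP*

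**What the plan says.** **Allocation.** SAP 3.3 states the overall ratio: "Eligible subjects will be randomly assigned in a 2:1:1:1 ratio to one of four treatment arms on Day 1, at the point of dosing". It then fixes the sentinel numbers: "four subjects for treatment arm 1, and two subjects from each of treatment arms 2, 3 and 4, will be dosed before the remaining subjects". Protocol 3.4.4 separates the cohorts in time, because blinded sentinel safety data up to Day 15 "will be reviewed by a Safety Review Committee (SRC) prior to dosing the 30 remaining participants". Protocol Table 7 also allows the remaining 30 to be subdivided: "they may be divided into two or more dosing groups, with the groups being dosed on different days". It adds a balance condition: "Each dosing group would contain a minimum of two participants from each of the four treatment arms".

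**Model.** The per-timepoint analysis in SAP 4.12 uses "a linear model with the two treatments (PYR and PQP) and their interaction as factors and baseline as covariate", fitted separately at each timepoint, with two-sided 90% intervals for each active treatment against placebo. Protocol 10.4.3 describes the same model. Neither document puts cohort, sentinel status or dosing group into this or any other model. The stratified presentation in SAP 4.1 is by body-weight group only.

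**Numbers.** SAP 3.2 says that recruitment stopped at 37. It does not give the split by arm or by cohort.

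**The concern.** When the allocation fixes treatment numbers inside a group, that group is a block, and the usual practice is to put it in the model. If it is left out and the blocks differ, the treatment estimate is unchanged as long as the arms are balanced within blocks. The between-block variation goes into the residual, though, so the stated standard error is larger than the design warrants.

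What is at stake is precision in the one QTc model that the plan commits to. SAP sections 1 and 4.12 make the concentration-QTc analysis optional, so the per-timepoint model carries the secondary QTc endpoint unless that analysis is done. SAP 4.12 itself concedes that the per-timepoint analysis has limited power to show that a prolonging effect is absent.

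The stop at 37 adds a smaller issue. If the shortfall is uneven across arms, cohort and treatment are no longer orthogonal, and part of a cohort difference can enter the treatment contrasts.

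**Working it through.** **The plan's own figure.** The only sample-size figures (SAP 3.2) are the probabilities of at least one event among 16 participants. 1 − 0.9^16 = 81.5% and 1 − 0.8^16 = 97.2%, matching the stated 81% and 97%. They do not concern QTc.

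**Inputs from the documents.** Planned arms are 16/8/8/8. The sentinel cohort is 4/2/2/2, which leaves 12/6/6/6 in the main cohort. The model has five parameters (intercept, PYR, PQP, interaction, baseline), so residual df = 40 − 5 = 35, or 34 with cohort. Intervals are two-sided 90%.

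**Assumptions.** The within-cohort residual SD is s = 8 ms. The cohort difference in baseline-adjusted QTc change is d = 0, 4 or 8 ms. Baseline costs one df and is otherwise unrelated to arm and cohort. None of these is in the documents.

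**Planned n=40.**
- Cohort sum of squares within arms: 4×12/16 + 3 × (2×6/8) = 3 + 4.5 = 7.5.
- Expected residual variance with cohort omitted: s² + d² × 7.5/35.
- Half-width for PQP minus placebo: t × √variance × √(1/8 + 1/8), where the last factor is 0.5. t(35) = 1.6896 and t(34) = 1.6909. Balance within cohorts leaves the 0.5 unchanged when cohort is added.

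| d (ms) | Residual variance, omitted | Half-width omitted (ms) | Half-width included (ms) | Change from adding cohort |
|---|---|---|---|---|
| 0 | 64.0 | 6.76 | 6.76 | 0.1% wider |
| 4 | 64 + 16×7.5/35 = 67.4 | 6.94 | 6.76 | 2.5% narrower |
| 8 | 64 + 64×7.5/35 = 77.7 | 7.45 | 6.76 | 9.2% narrower |

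A simulation of combination minus placebo (4,000 runs per setting, s = 8 ms) agrees. With cohort omitted, bias stays within 0.1 ms, while coverage of the nominal 90% interval rises to 92.0% at d = 6 ms and 93.4% at d = 8 ms. With cohort included, coverage is about 90%.

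**n=37.** Assume that the sentinel cohort is complete and the three missing participants belong to the main cohort. The bias from omission is d times the difference between the two arms in main-cohort share.
- All three missing from placebo: shares are 6/8 = 0.75 for PQP and 3/5 = 0.60 for placebo, a difference of 0.15. The bias is 0.6 ms in size at d = 4 and 1.2 ms at d = 8. The combination share is 12/16 = 0.75, so that contrast is affected equally. Losing all three from PQP instead gives the same size with opposite sign, but only in the PQP contrast.
- Missing spread to leave 11/6/5/5 in the main cohort: the bias is 0 for PQP minus placebo (5/7 in both arms). The largest is for PYR minus placebo, (6/8 − 5/7) × 4 = 0.14 ms at d = 4, or 0.29 ms at d = 8.
- Cost of adding cohort if d = 0, with all three missing from placebo: the cohort sum of squares is 3 + 1.5 + 1.5 + 2×3/5 = 7.2, so the variance factor gains 0.15²/7.2 = 0.0031. For combination minus placebo it goes from 1/16 + 1/5 = 0.2625 to 0.2656. With t moving from 1.6939 (32 df) to 1.6955 (31 df), the interval is 0.7% wider. For PQP minus placebo it is 0.6% wider.

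**The case against.** The strongest reply is that nothing in the documents suggests that the cohorts will differ in QTc change. Both are studied at one centre, with the same fasting, meal times, supine rest and triplicate ECGs on Days 1 to 3, and with over-readers blinded to date and treatment. The outcome is change from a three-timepoint Day 1 baseline, and baseline is also a covariate, so cohort differences in QTc level largely cancel. The SD and the cohort differences used here are assumed, and a difference of 8 ms is a full residual SD. No decision rule hangs on these intervals: the 10 ms criterion belongs to the concentration-QTc model. All of this stands, and it keeps the point small. It does not explain why a block set by the design is left out when including it costs almost nothing.

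A reader might look for a concrete mechanism in the visit setting. The note to protocol Figure 2 says "The Day 6 OP visit will apply to the non-sentinel group only", which would put sentinel participants in-house and the others in outpatient care that day. The documents do not support relying on this. Early discharge of the main group was conditional, and the note to SAP Figure 1 records that both groups stayed in-house until Day 7. For the same reason Day 7 should not be treated as a sentinel-only timepoint.

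A reader might also infer that the treatment contrasts are biased or the intervals too narrow. Under the planned 2:1:1:1 balance in both cohorts there is no bias, and the intervals err on the wide side.

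**Conclusion.** The point holds as a low-severity matter of precision. Cohort restricts the allocation, the cohorts are dosed about two weeks or more apart, and the per-timepoint model ignores this. Any cohort difference in baseline-adjusted QTc change inflates the error term. The loss is nil if the cohorts do not differ. With an assumed SD of 8 ms, adding cohort would narrow the interval by about 2.5% for a 4 ms difference and about 9% for 8 ms.

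Bias arises only through the unknown split of the 37. It ranges from 0 to about 0.6 ms (4 ms difference) or 1.2 ms (8 ms difference). The upper end requires all three missing participants to come from a single eight-person arm of the contrast, with main-cohort placebo the case that affects every contrast. The documents do not say that this happened. The analysis is secondary, in an exploratory trial, and no conclusion is shown to change.

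**What to change.** Add dosing cohort (sentinel or main) as a fixed factor to the per-timepoint QTc model in SAP 4.12, at every timepoint where both cohorts contribute data. Otherwise, state why it is left out. If the main group was split and actual dosing group is used instead, say so in advance.

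The cost is one term in the model statement and one degree of freedom: about 0.1% of interval width at n=40, and up to 0.7% at n=37 if the cohorts do not differ. Each additional dosing group costs one further degree of freedom. Cohort membership is already known, so no new data are needed. Reporting the 37 by arm and cohort would also show whether any imbalance exists. This is a nearly free improvement.

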### Hysteresis

Hysteresis between the effect of each of the monotherapies and its concentration will be investigated based on the results of the per timepoint analysis and the mean concentrations under these therapies. These time courses will be displayed in two or three panels respectively using the same time axis and, in addition, as hysteresis loops, separately for Day 1 and Day 3. Finally the enGRI [4] may also be calculated.

### Concentration-QTc analysis

Concentration-QTc analysis is optional and will be performed in future, as required. It might be based on a separate analysis plan and reported in an addendum to the final CSR or a separate report, as appropriate.

This analysis will be based on the change of QTc from baseline and will use baseline QTc (centred on the mean across subjects) and the concentrations of PYR and PQP as covariates. Concentrations of relevant metabolites may also be included. Interaction between concentrations of PYR and PQP will also be included. Interaction terms with metabolites, if any, will not be used.

Concentrations BLQ will be set to nought. Likewise, concentrations for participants under placebo will be set to nought, as well as those for the drug not given to a participant.

Treatment with levels Placebo, PYR, PQP and combination (referred to as "treatment intercept" in the sequel) and time will be used as discrete fixed effects.(Note that the same timepoint at different days will be considered distinct.) A series of linear models including one or more of the concentrations will be fitted. The model including both moieties will have the form (in the notation of lmer in R):

$$dQTc \sim TP + trt + CPYR*CPQP + Cbl -1 + (1 + CPYR + CPQP|Subj)$$

where

- dQTc is the change from baseline of QTc
- TP is the factor describing timepoints
- trt is the treatment intercept
- CPYR is the concentration of PYR
- CPQP is the concentration of PQP
- Cbl is the centered baseline
- Subj is the factor describing participants (as unit of observation).

From this model simplified models will be derived by removing one of the concentrations variables.

The most appropriate one will be selected based on the Akaike Information Criterion (AIC) and the size of the fixed treatment effect. A significant treatment effect (based

on an F-test,  $p < 0.05$  two sided) will be considered an indication for model misfit. For the best fitting linear model, predictions of the effect on  $QT_c$  will be made. These predictions will be made separately for each treatment group and will be based on the mean concentrations of all moieties involved in the respective model.

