#### **10.4.5 Concentration- $QT_c$ analysis**

This analysis will be based on the change of  $QT_c$  from baseline and will use baseline  $QT_c$  (centred on the mean across participants) and the concentrations of PYR and PQP as covariates. Concentrations of relevant metabolites may also be included. Treatment with levels Placebo, PYR, PQP and combination (referred to as "treatment intercept" in the sequel) and time will be used as discrete fixed effects. A series of linear models including one or more of the concentrations will be fitted and the most appropriate one will be selected based on the Akaike Information Criterion (AIC) and the size of the fixed treatment effect. A significant treatment effect (based on an F-test) will be considered an indication for model misfit. For the best fitting linear model, predictions of the effect on  $QT_c$  will be made. For these predictions, the  $T_{max}$  of every moiety included in the model will be determined and the mean concentration of all moieties involved at these timepoints will be used. Details of the model selection procedure and the concentrations to be included in the best fitting model will be given in the SAP.

Linearity of the concentration- $\Delta QT_c$  relationship will be explored based on quantile plots as described in Garnett et al (2018) [20]. In addition, a significant treatment intercept can be interpreted as sign of either hysteresis or nonlinearity. If the best fitting linear model has a significant treatment effect, nonlinear e-max models will also be considered, and predictions will be made based on the best fitting model. In this case, hysteresis between  $QT_c$  and the concentrations of the relevant analytes will be investigated graphically.

Absence of an effect of concern of the IMP on  $QT_c$  will be concluded if the predictions based on the best-fitting model at the concentrations described above exclude an effect exceeding 10 ms, i.e. the upper limit of the two-sided confidence interval for these predictions is below 10 ms.

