## 3. TRIAL DESIGN

### 3.1 Overall Trial Design

This will be a single-centre, randomised, double-blind, placebo-controlled, parallel group study to determine the safety, tolerability and PK of the registered dose to treat acute uncomplicated malaria of PYR + PQP, PYR + PQP placebo, PYR placebo + PQP, as well as PYR placebo + PQP placebo when administered orally once daily for three days to healthy adult male and female participants.

Forty (40) participants are planned to be enrolled and randomised to one of the four treatments in a 2:1:1:1 ratio as described below:

- Treatment 1 (N=16): PYR + PQP
- Treatment 2 (N=8): PYR + placebo for PQP
- Treatment 3 (N=8): placebo for PYR + PQP
- Treatment 4 (N=8): placebo for PYR + placebo for PQP

All participants will receive a single dose of PYR or placebo, as well as a single dose of PQP or placebo, on the morning of Day 1, Day 2 and Day 3. Participants will fast for at least three hours prior to dosing and four hours after dosing. Within

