## 3.2 Sample Size

This is an exploratory trial and the sample-size is not based on formal statistical considerations. The numbers assigned to each treatment group are considered adequate to describe the tolerability, safety and pharmacokinetics.

Assuming that an event occurs in 10% of the cases, the probability to see at least one case in 16 subjects on combination treatment is 81%. If the event occurs in 20% of the cases, this probability increases to 97%.

Participants recruitment has stopped at 37.

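### The SAP's candidate concentration-QTc models omit the additive PYR + PQP model, so AIC must choose between an interaction model and dropping a drug

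*SAP*

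**What the plan says.** SAP 4.12 (Concentration-QTc analysis) writes the model with both drugs as "TP + trt + CPYR*CPQP + Cbl -1 + (1 + CPYR + CPQP|Subj" with the bracket then closed. In that notation `CPYR*CPQP` expands to both main effects plus their product. The text confirms this: "Interaction between concentrations of PYR and PQP will also be included". Simpler candidates come from one rule: "From this model simplified models will be derived by removing one of the concentrations variables". The list of terms under the formula defines two concentration variables, CPYR and CPQP; the product has no entry of its own.

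Protocol 10.4.5 uses the two concentrations as covariates and says "A series of linear models including one or more of the concentrations will be fitted". It mentions no interaction in this analysis and leaves the details of model selection to the SAP.

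Both documents select by AIC together with the size of the treatment effect, and read a significant treatment F-test as misfit. The selected model serves two decisions. An effect of concern is ruled out if the upper confidence limit of the predictions is below 10 ms. Assay sensitivity is judged by comparing the PQP effect with 0.0475 ms/(ng/mL). The SAP calls the analysis optional and allows it a separate plan.

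**The concern.** The secondary ECG objective has three parts: the PQP relationship, the PYR relationship, and the impact of combining them. The simplest description of two drugs that both act without interacting is the additive model, and it is not on the list. AIC therefore never compares both drugs without interaction against both drugs with it. It must either carry a product term or discard a drug.

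Each choice has a cost. Carrying an unneeded product term makes the slopes less precise. Discarding PYR leaves the PYR arm with no concentration term, although that arm's prediction still enters the 10 ms conclusion.

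**Working it through.** **1. The candidate set.** Start from `CPYR + CPQP + CPYR:CPQP`. Removing CPYR also removes the product and leaves CPQP. Removing CPQP leaves CPYR. No permitted step removes the product alone, so `CPYR + CPQP` is unreachable.

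**2. Is there a planned figure to reproduce?** Not for this analysis. The only design figure (SAP 3.2) reproduces: 1 - 0.9^16 = 81.5% and 1 - 0.8^16 = 97.2%, against 81% and 97%.

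**3. Slope precision when there is no interaction.** For each model, Var(β) = (X'V⁻¹X)⁻¹, with timepoint, treatment intercept, centred baseline and random effects as in the SAP. Inflation is SE(interaction model) / SE(additive model) - 1.

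- From the documents: allocation 16/8/8/8; recruitment stopped at 37; times in protocol Tables 5 and 6; PYR peak 2-8 h and half-life 14-18 days; PQP peak about 5 h and half-life about 22 days.
- Assumed: concentration CV 30, 50 or 70%; exposure correlation 0 or 0.5; residual SD 5-8 ms; intercept SD 5-6 ms; random slopes from none to large; sampling to Day 4 or Day 22; 15/7/7/8 for the 37.

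| Case (Day 22 sampling unless stated) | PYR slope SE | PQP slope SE |
|---|---|---|
| CV 30%, moderate random slopes | +29% | +27% |
| CV 50%, moderate random slopes | +24% | +20% |
| CV 70%, moderate random slopes | +19% | +14% |
| CV 50%, no random slopes | +35% | +32% |
| CV 50%, large random slopes | +17% | +10% |
| All 120 scenarios (both sampling lengths): lowest, middle, highest | +9.7, +25.9, +37.4% | +5.9, +23.3, +39.5% |

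The inflation is positive for both slopes in all 120 scenarios. At +24% the information about the PYR slope is 1/1.24² = 0.65 of what the additive model gives. The reason is that each slope in the interaction model is the slope at zero concentration of the other drug. That leans on the 8 monotherapy participants, where the additive model uses all 16 + 8 = 24 who take the drug.

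**4. Precision of the 10 ms predictions.** Over the same 120 scenarios the prediction SE rises by 0 to 3.6% (combination), 0 to 4.0% (PYR alone) and 0.1 to 5.7% (PQP alone). A separate calculation under other assumed profiles gave 0-4%, 0-3% and 1-8%. Most of the slope loss cancels at the concentrations where predictions are made.

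**5. If PQP-only is selected.** The SAP sets the concentration of a drug not given to zero, so CPQP = 0 throughout the PYR arm. The predicted difference from placebo is then trt(PYR) - trt(placebo), one constant averaged over all timepoints.

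The plan makes this choice easier. From PQP-only to the interaction model there are two more fixed effects and, with an unstructured 3×3 instead of 2×2 covariance, 6 - 3 = 3 more variance parameters. The AIC penalty is 2 × 5 = 10. To the additive model it would be 2 × 4 = 8.

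Two sets of simulated trials used additive truth, 16/8/8/8, 28 timepoints, a PQP effect of 17 ms (protocol section 1 gives 15-20 ms fasted), SDs of 5 ms between participants and 6 ms residual, and ML-based AIC. Set A had 90 trials per effect and unstructured random effects. Set B had 40 trials per effect, diagonal random effects and concentration CV 40%.

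| True PYR effect at Cmax | Plan selects PQP-only | PYR-arm prediction from PQP-only |
|---|---|---|
| 3 ms, set A | 72% | 2.0 ms (67%) |
| 3 ms, set B | 21/40 (53%) | 1.7 ms (57%) |
| 5 ms, set A | 23% | 3.2 ms (64%) |
| 5 ms, set B | at most 4/40 (36/40 chose interaction) | 3.5 ms (70%) |

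A direct least-squares calculation gives about 60-65%. In set B the treatment F-test flagged the PQP-only model in 10% of trials at 3 ms and 25% at 5 ms. With the additive model offered at 3 ms, PQP-only fell to 16/40 and additive took 22/40.

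**6. What AIC does once the additive model is offered.** It keeps the product only if |t| exceeds √2 = 1.41. With no interaction that happens with probability 2[1 - Φ(1.41)] ≈ 16%, so additive beats interaction about 84% of the time. The simulations gave 82% (A, 8 ms), 32/40 (B, 5 ms) and 35/40 (B, 8 ms). Conversely, a true 4 ms interaction at joint Cmax would be dropped in about 7-51% of trials, depending on assumed variability.

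**The case against.** The case for leaving the list alone has substance.

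- **The objective can be addressed as written.** A reader might infer that the PYR, PQP and combination effects cannot be separated without an additive model. The documents do not support that: the interaction model has a term for each, SAP 4.12 tabulates every coefficient with its 90% CI, and the per-timepoint model also has an interaction.
- **The product term has a purpose.** SAP 4.12 says the analysis centres on the known QTc prolongation and any influence of PYR on it. This is a good reason to keep the interaction model, but not to leave out the additive one.
- **The 10 ms predictions are not made materially imprecise.** Step 4 bears this out. For the arms with PQP, an upper limit below 10 ms is implausible under any candidate given the 15-20 ms the protocol cites. The PYR-alone arm is where the decision could change.
- **AIC is not the only selection criterion.** The size of the treatment effect and the F-test also count, and a significant effect leads to Emax models. The simulated selection rates use AIC alone, so they indicate direction rather than the plan's actual error rates. Monte Carlo error is also large: √(0.72 × 0.28/90) ≈ 5 points in set A, and √(0.525 × 0.475/40) ≈ 8 points in set B. Even so, an F-test that flags 10-25% of the affected fits is only a partial safeguard.
- **Protocol 10.4.5 is not contradicted outright.** It defers model selection to the SAP. The omission is an unexplained narrowing.
- **The analysis is optional** and may be re-specified. That lowers the urgency, but SAP 4.12 is the specification that stands now.

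**Conclusion.** The additive model is missing from the candidate list; this follows from the SAP text alone. Two consequences follow, both conditional.

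First, if the drugs do not interact and the interaction model is selected, both slope standard errors grow by roughly 6-40%. This affects slope reporting and the PQP slope used for assay sensitivity. A narrower band such as 22-29% might be inferred from one set of assumptions, but both slopes fell inside it in only 20% of the 120 scenarios. The documents give no variance component or concentration variability that would fix the figure. The prediction standard errors grow by about 0-8%.

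Second, and more important for the 10 ms rule, a real PYR effect of about 3-5 ms can end in a PQP-only model. The PYR-arm prediction then recovers about 60-65% of the effect at PYR Cmax (57-70% across the simulated cases), under assumed PK profiles. Adding the additive model makes this less frequent but does not remove it, so a rule on the source of PYR predictions is also needed.

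The change should be made before the analysis is run.

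**What to change.** In SAP 4.12, or in the separate plan if one is written:

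1. Add to the candidates, between the full and one-drug models: `dQTc ~ TP + trt + CPYR + CPQP + Cbl - 1 + (1 + CPYR + CPQP|Subj)`.
2. State that any prediction about PYR, alone or in combination, comes from a model that contains CPYR, even if AIC prefers PQP-only.
3. State that the interaction estimate and its 90% CI from the full model are always reported, whichever model AIC selects.
4. Note how the list now relates to protocol 10.4.5.

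The cost is one more fit and a few sentences, with no new data. The change is not free of downside: AIC may now drop a modest true interaction, and combination predictions would then omit it. Item 3 mitigates this by keeping the interaction estimate in view.
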